3.5.1.1 Adverse events of special interest

The following AESIs will be particularly monitored in this study:

- Hepatic function abnormality meeting the definition of Hy's Law as described in Section 8.3.8 of the protocol.
- Serious hypersensitivity (including Type 1 to 4 hypersensitivity reactions), for example anaphylaxis and severe allergic reactions, and immune complex disease.
- Injection site reactions.
- Cardiac events (including angina or myocardial infarction, congestive heart failure, symptomatic atherosclerotic vascular disease, cor pulmonale, or arrhythmia).
- Serious infections (including opportunistic infections and viral reactivations), for example herpes simplex virus/varicella zoster virus, Epstein Barr virus/cytomegalovirus, TB, SARS-CoV-2 and all other opportunistic infections listed in the Guidelines for the Prevention and Treatment of Opportunistic Infections in Adults and Adolescents with HIV.
- Gastrointestinal adverse events.
- Malignancy.

AEs will be assigned to a specific category based on investigator's judgement, using a checkbox on the AE CRF page. In addition, standardized MedDRA queries (SMQs) will be utilized when possible, and a selection of HLTs, SOCs and/or PTs will be utilized to represent other situations, to perform a cross-check with eCRF categories. A comprehensive list will be provided by the patient safety team prior to any study delivery.

3.5.2 Vital signs variables

Vital signs assessments (body temperature, diastolic blood pressure (DBP), systolic blood pressure (SBP), heart (pulse) rate and respiratory rate) will be performed at visits SV1, SV4, SV6, SV7, SV8, SV9, SV10, SV11, SV12 and E/D. For SV4 and SV7 vital signs will be taken before and immediately after administration of study intervention, and at 30, 60, and 120

minutes (± 5 minutes). For SV8 and SV9 vital signs will be taken before and immediately after administration of study intervention, and at 30 and 60 minutes (± 5 minutes) thereafter.

Height will be assessed at SV1 only. Weight will be assessed at SV1, SV4, SV10, SV12 and E/D.

Body mass index will be calculated from the height (in meters) and weight (in kilograms) as follows: $BMI = \text{weight} / (\text{height}^2)$.

Additionally, vital signs values will be classified as normal (if value is between lower and upper limit), low (if value is below the lower limit), and high (if value is above the upper limit) according to the normal reference ranges (Table):

Table 17 Vital sign reference ranges

Parameter	Standard Unit	Lower limit	Upper limit	Change Criteria
Body temperature	$^{\circ}\text{C}$		>37	± 1
DBP	mmHg	<60	>100	± 15
SBP	mmHg	<90	>160	± 30
Heart (pulse) rate	beats/min	<50	>100	± 20
Respiratory rate	breath/min	<12	>24	± 3
BMI	kg/m^2	<18.5	≥ 35	

High value (H) is defined as upper reference limit. High change (HC) is defined as increase from baseline greater than prespecified criterion. Low value (L) is defined as below lower reference limit. Low change (LC) is defined as decrease from baseline greater than prespecified criterion.

3.5.3 Laboratory variables

Clinical Safety Laboratory will be performed at visits SV1, SV4, SV6, SV7, SV8, SV9, SV10, SV12 and E/D, except for urinalysis that will be performed at visits SV1, SV4, SV6, SV7, SV8, SV9, SV10 and E/D. Clinically significant abnormal laboratory results are defined by the investigator.

Following haematology, clinical chemistry and urinalysis parameters will be assessed:

Table 18 Laboratory safety variables

Haematology/Haemostasis (whole blood)	Clinical Chemistry (serum or plasma)
WBC count with differential	Potassium
RBC count	Sodium
Haematocrit	AST
Platelet count	ALT

Haemoglobin	ALP
Coagulation parameters (PT, INR, and aPTT)	TBL (if result is > 1.5 ULN, indirect and direct bilirubin will be measured)
	GGT
Urinalysis (dipstick)	Creatinine
Colour and appearance	Blood urea nitrogen
Specific gravity	Albumin
pH	Total protein
Protein	Uric acid
Microscopy including WBCs, RBCs, and casts.	
Glucose	
Ketones	
Blood	
Bilirubin	
Leukocytes	

Note for haematology: blinding procedures for eosinophil, basophil, and monocyte data are described in Section 6.3.2 of the protocol.

Note for serum chemistry: Tests for AST, ALT, ALP, and TBL must be conducted concurrently and assessed concurrently.

ALP = alkaline phosphatase; ALT = alanine transaminase; aPTT = activated partial thromboplastin time; AST = aspartate transaminase; GGT = gamma glutamyl transferase; Ig = immunoglobulin; INR = international normalised ratio; PT = prothrombin time; RBC = red blood cell; TBL = total bilirubin; ULN = upper limit of normal; WBC = white blood cell.

3.5.3.1 Other safety tests

- NT-proBNP (only at SV1, SV8, SV9, SV10, SV12 and E/D)
- SARS-CoV-2 PCR test (performed anytime between Day -7 and Day -4 as the results are needed prior to randomisation. Testing may then be performed at any point during the study intervention and follow-up periods for a participant suspected of having COVID-19)

3.5.3.2 SARS-CoV-2 serology testing

Participants' serum will be tested for the presence of antibodies to the SARS-CoV-2 virus from blood drawn at the visits SV4, SV10 and E/D.

3.5.4 Electrocardiogram (ECG)

ECG variables will be collected at visits SV1, SV4, SV10, SV12, and E/D as follows:

- Heart (pulse) rate
- RR interval
- QRS interval

- PR interval
- QT interval

Additionally, QT correction using Bazett's and Fridericia's formulas will be calculated as follows (unless already derived directly from the CRF):

$$QTcB = QT/(RR^{1/2}),$$

$$QTcF = QT/(RR^{1/3}),$$

where QT is measured in msec and RR is measured in sec.

Categorical ECG interpretation (normal, abnormal clinically significant, abnormal not clinically significant) will be provided by the investigator.

Table 19 ECG reference ranges

Parameter	Standard Unit	Lower limit	Upper limit	Change criteria
Heart (pulse) rate	beats/min	<50	>100	
RR interval	ms	<600	>1200	
QRS interval	ms	<80	>120	
PR interval	ms	<120	>200	
QT interval	ms	N/A	>450 male >470 female	+30
QTcB interval	ms	N/A	>450 male >470 female	+30
QTcF interval	ms	N/A	>450 male >470 female	+30

3.5.5 Echocardiogram

A transthoracic echocardiogram to assess left ventricular ejection fraction (LVEF) will be assessed any time after signing of informed consent, so that results are available prior to randomisation and then at any time at or between SV9 and SV10 inclusive.

3.6 Derivation of exploratory variables

3.6.1 Airwave oscillometry (AO) variables

Airwave oscillometry will be performed at SV2, SV4, SV6, SV7, SV8, SV9 and SV10. Airwave oscillometry is a non-invasive lung function test included in this study to evaluate treatment effect on small airway physiology.

The parameters R5, R20, R5-R20 and AX for each assessment will be recorded and analysed. The AO assessment at SV6, SV7, SV8, SV9, and SV10 will be performed only if the baseline visit AO is performed successfully, as judged by the investigator.

3.6.2 Patient reported outcome (PRO) variables

Patient-reported outcome data will be captured via an ePRO device. For all outcomes based on the ePRO devices, analyses will be based on data up to and including Week 24.

For asthma symptom score, rescue medication use and home peak expiratory flow, 2-weekly means will be calculated. A 2-weekly mean is calculated as the sum of all non-missing daily measures/scores over 14 sequential days divided by the number of days with non-missing measures/scores. For nights with awakenings due to asthma, the 2-weekly mean will be the percentage of times the participant answered “yes” to ‘did your asthma cause you to wake up’ and “yes” to ‘did you use rescue medication upon awakening’. For derivation of the 2-weekly mean scores see Section 3.1.4. Note that the first 2-weekly mean in the treatment period will be based on the evening recording on day 1 up to and including the morning recording on day 15. The daytime score is recorded in the evening and the night-time score is recorded the following morning; 2-weekly periods are defined as follows (where Day 1 is the day of randomisation)

Where a total score is calculated within a day (e.g. Asthma symptom score), this calculation will span two calendar days – the daytime value recorded in evening of day X, and the night-time value recorded on morning of day x+1. E.g. the asthma symptom score on Day 1 will be the day time score recorded on the evening of Day 1 + the night-time score recorded on the morning of Day 2.

Where only night-time scores/results are of interest, the morning entries on the second day of a period up to and including the morning entry on the last day of the period (or morning of the last day of study for the last period/last IP intake) will be considered. Where only daytime scores/results are of interest, the evening entries on the first day of the period up to and including the evening entry on the second last day of the period (or evening before the last day of study/last IP intake) will be considered.

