To assess the longitudinal effect of MEDI3506 compared with placebo on lung function in adult participants with uncontrolled moderate-to-severe asthma.	As measured in clinic, change from baseline in pre-BD FEV1 to Weeks 1, 4, 8, 12, 20, and 24.
To assess the acute effect of MEDI3506 compared with placebo on pre-BD FEV1 in adult participants with uncontrolled moderate-to-severe asthma.	As measured in clinic, change in pre-BD FEV1 (L) from pre-administration of study intervention to 4 hours post-administration of MEDI3506 or placebo at Day 1.
To assess the effect of MEDI3506 compared with placebo on asthma control in adult participants with uncontrolled moderate-to-severe asthma.	During the intervention period (baseline to Week 16): 
 • Annualised rate of asthma exacerbations. • Annualised rate of hospitalised asthma exacerbations.
To assess the longitudinal effect of MEDI3506 compared with placebo on asthma control and health status in adult participants with uncontrolled moderate-to-severe asthma.	Change from baseline to Weeks 1, 4, 8, 12, and 24 in ACQ-6 score. Change from baseline to Weeks 4, 12, and 24 in SGRQ score. Change from baseline up to Week 24 in 2-weekly mean daily rescue medication usage (puffs/day). Change from baseline to Weeks 4, 8, 12, 16, 20, and 24 in: 
 • Asthma symptom score. • Mean number of night-time awakenings.
To assess the benefit-risk profile of MEDI3506 as perceived by adult participants with uncontrolled moderate-to-severe asthma.	PGI-BR at Week 16.
To evaluate CCI and inflammatory blood biomarkers that may predict an efficacy response to MEDI3506 in adult participants with uncontrolled moderate-to-severe asthma.	CCI  Association of allergen-specific IgE status with primary and secondary efficacy endpoints at Week 16.
To assess the effect of MEDI3506 compared with placebo on asthma related inflammatory airway biomarkers in adult participants with uncontrolled moderate-to-severe asthma.	Percent change from baseline to Weeks 1, 4, 8, 12, 16, 20, and 24 in concentration of FeNO. Change from baseline to Weeks 4, 8, 12, 16, 20, and 24 in exploratory biomarkers measured in nasal lining fluid. Change from baseline to Week 16 in mRNA nasal transcriptome.

Table 4 Objectives and Endpoints

Objective	Endpoint

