8.1.8.1 Daily eDiary

During the study period, participants will be required to take their asthma controller therapy regularly and complete an eDiary twice daily.

At SV1, participants will receive a handheld eDiary device to complete twice-daily, daily and non-daily PRO assessments during the study. Participants will be provided training on the use of the handheld device. Daily assessments will include night-time and daytime asthma symptoms (morning and evening diary, respectively), use of inhaled rescue medication in response to worsening symptoms, nights with awakenings due to asthma symptoms (morning diary only) and background medication use. The PEF data (obtained from the home peak flow meter) will be captured at the conclusion of the morning and evening eDiary entry.

Daytime is defined as the time period between the morning lung function assessment (upon rising in the morning) and the evening lung function assessment. Night-time is defined as the time period between the evening lung function assessment (at bedtime) and the morning lung function assessment.

The number of doses of rescue medication (1 dose unit = 1 puff on inhaler) taken will be recorded by the participant in the eDiary twice daily. The number of inhalations taken between the morning and evening lung function assessments will be recorded in the evening. The number of inhalations taken between the evening and morning lung function assessments will be recorded in the morning.

Nocturnal awakenings due to asthma symptoms will be recorded by the participant in the daily eDiary each morning by answering the question whether he/she woke up during the night due to asthma symptoms by a “yes” or “no” response.

Background (inhaled ICS/LABA) medication administration use will be recorded once daily in the daily eDiary as “yes” or “no” response.

The eDiary questions support the analysis of a novel endpoint called CompEx (Section 8.1.6).

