3.6.2.3 Nights with awakening due to asthma

Bi-weekly mean change from baseline in the number (percentage) of nights with awakening due to asthma that required rescue medication will be calculated as the outcome variable for the 2-weekly periods according to Table 1 (Section 3.1.4).

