6 CHANGES OF ANALYSIS FROM PROTOCOL

This SAP is based on study protocol D9181C00001 Amendment V4.0 dated 08 March 2022. Any further amendment of the study protocol which can have an impact on the SAP will lead to an amendment of this document. Changes of analysis from D9181C00001 Amendment V4.0 dated 08 March 2022 are listed here below:

Section 3 Objectives and endpoints

- Time to first CompEx event based on the period from baseline to Week 16 is a secondary endpoint for this study. However, in this SAP, a supplementary analysis including events on the period from baseline to end of follow-up (Week 24) has been added.
- An additional spirometry parameter not part of the main study endpoints (FEF25-75%) will be explored.

Section 8.1.8.3 Asthma Control Questionnaire-6

In this section it is stated that “Mean scores of ≤ 0.75 indicate well-controlled asthma, scores between 0.75 and ≤ 1.5 indicate partly controlled asthma, and scores > 1.5 indicate not well-controlled asthma”. In this SAP it is specified that “Mean scores of ≤ 0.75 indicate well-controlled asthma, scores between >0.75 and <1.5 indicate partly controlled asthma, and scores ≥ 1.5 indicate not well-controlled asthma”.

Section 9.4.2.1 Primary Endpoint

In this section it is stated that the MMRM will include “fixed effects for baseline, visit, treatment and the baseline by visit and treatment by visit interactions”. In this SAP it is mentioned that the MMRM will additionally include background medication, geographic region and baseline ICS total daily dose as fixed effects. The same variables will be added as covariates to ANCOVA, logistic regression, Cox proportional hazards and negative binomial models.

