14.2 Exploratory Diary + ePRO		
Table 14.2.8.1	2-weekly mean daily rescue medication usage (puffs/day) through Week 24, summary statistics	ITT population
Table 14.2.8.2	Change from baseline through Week 24 in 2-weekly mean daily rescue medication usage treatment comparisons, MMRM	ITT population
Figure 14.2.8	Change from baseline through Week 24 in 2-weekly mean daily rescue medication usage, LSMeans (80% CI)	ITT population
Table 14.2.9.1	2-weekly mean asthma symptom score through Week 24, summary statistics	ITT population

Table 14.2.9.2	Change from baseline through Week 24 in 2-weekly mean asthma symptom score treatment comparisons, MMRM	ITT population
Figure 14.2.9	Change from baseline through Week 24 in 2-weekly mean asthma symptom score, LSMeans (80% CI)	ITT population
Table 14.2.10.1	2-weekly mean number of night time awakenings through Week 24, summary statistics	ITT population
Table 14.2.10.2	Change from baseline through Week 24 in 2-weekly mean number of night time awakenings treatment comparisons, MMRM	ITT population
Figure 14.2.10	Change from baseline through Week 24 in 2-weekly mean number of night time awakenings, LSMeans (80% CI)	ITT population
Table 14.2.11	PGI-BR responses at Week 16	ITT population

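### The exploratory endpoint named as night-time awakenings is analysed as nights with an awakening plus rescue use, so the named endpoint is never analysed and its outputs are mislabelled

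*SAP*

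**What the plan says.** **Named endpoint.** Protocol Section 3 (Table 4) lists change from baseline to Weeks 4, 8, 12, 16, 20 and 24 in "Mean number of night-time awakenings" among the exploratory endpoints. SAP Section 1.1 (Table 1) repeats it, and SAP Section 3.1.1 uses the same name when it sets the 14-day diary baseline. None of these mentions rescue medication.

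**Data collected.** Protocol Section 8.1.8.1: "Nocturnal awakenings due to asthma symptoms will be recorded by the participant in the daily eDiary each morning". The answer is a single yes or no per night, and the description of the item carries no rescue condition.

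**Variable derived.** SAP Section 3.6.2 takes a percentage of nights on which "the participant answered “yes” to ‘did your asthma cause you to wake up’ and “yes” to ‘did you use rescue medication upon awakening". SAP Section 3.6.2.3 confirms that the two answers are joined: its outcome variable is the number (percentage) of "nights with awakening due to asthma that required rescue medication".

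**Outputs.** SAP Appendix C titles Table 14.2.10.1 "2-weekly mean number of night time awakenings through Week 24, summary statistics". Table 14.2.10.2 and Figure 14.2.10 use the same name.

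**Declared changes.** SAP Section 6 states: "Changes of analysis from D9181C00001 Amendment V4.0 dated 08 March 2022 are listed here below". It lists the added CompEx analysis to Week 24, an extra spirometry parameter, the ACQ-6 category boundaries and the added model covariates. Awakenings are not mentioned there or in the SAP amendment history.

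**The concern.** One name covers two different quantities. A reader of Tables 14.2.10.1 and 14.2.10.2 would take the result as evidence about waking at night. The variable behind it also depends on whether the participant used a reliever after waking, and nothing in the title says so.

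Two things follow. If the arms differ in how often an awakening leads to rescue use, the table can show fewer awakenings when nights with an awakening are unchanged. If treatment reduces awakenings that did not lead to rescue use, the table does not register it. Rescue use already has its own exploratory endpoint under the same objective, so the two results would partly overlap without the reader knowing.

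What is at stake is the correct reading of one exploratory diary endpoint. It is, however, modelled by MMRM through Week 24 (SAP Section 4.2.6.6), with one-sided p-values and 80% intervals (SAP Section 4.1.2).

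**Working it through.** The plan states no figure for this endpoint, so there is none to reproduce. The check has two parts.

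**1. Comparing the definitions for a single night**

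| Night | Diary waking item (Protocol 8.1.8.1) | SAP 3.6.2 variable |
|---|---|---|
| Not woken by asthma | No | No |
| Woken, rescue used on awakening | Yes | Yes |
| Woken, no rescue used | Yes | **No** |

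The third row is the whole discrepancy. The text in SAP 3.6.2 cannot reasonably be read as two separate percentages, because 3.6.2.3 defines one outcome with rescue use built in. SAP Section 4.2.3.6 also summarises awakening and rescue use jointly at baseline.

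Count versus percentage is a smaller mismatch. With one yes/no per night, a number of awakenings can only mean a number of nights, and over 14 recorded nights that is a rescaling of the percentage.

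**2. How the derived variable behaves**

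Let *a* be the proportion of nights with an awakening and *r* the probability of rescue use given an awakening.

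- SAP variable = *a* × *r*
- If *a* is equal in both arms, the difference (active minus placebo) = *a* × (*r*₁ − *r*₀), and the relative difference = *r*₁/*r*₀ − 1
- If *r* is equal in both arms and stable over time, the difference = *r* × (*a*₁ − *a*₀). This shrinks the true contrast and creates no false one.

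The documents give neither *a* nor *r*, so the values below are assumptions, with equal baselines in the two arms. In every cell the true difference in nights with an awakening is zero.

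| *a* (both arms) | *r*: 0.9 placebo, 0.8 active | *r*: 0.8 placebo, 0.6 active | *r*: 0.8 placebo, 0.4 active |
|---|---|---|---|
| 20% | −2 points | −4 points | −8 points |
| 40% | −4 points | −8 points | −16 points |
| 60% | −6 points | −12 points | −24 points |
| Relative difference | −11.1% | −25% | −50% |

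The middle cell worked through: 0.40 × 0.80 = 32% on placebo and 0.40 × 0.60 = 24% on active, a difference of −8 points. Per 14 nights, that is 4.48 versus 3.36 nights, while both arms actually woke on 14 × 0.40 = 5.6 nights.

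**The case against.** The strongest reply is that the SAP filled in a definition rather than changed one. The protocol gives only a label for this endpoint, and its Section 9.4.5.3 leaves the detail of exploratory analyses to the SAP. The rescue-conditioned form is also the protocol's own construct, since Section 8.1.5 uses it in the eDiary criteria for worsening asthma. The SAP states its derivation openly, in two places.

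Much of this stands. The composite is a recognisable measure, it is not concealed, and whether Section 6 strictly had to list it can be argued. But the protocol never links the Section 8.1.5 criterion to this endpoint. Freedom to specify the detail also does not explain why SAP Table 1, Section 3.1.1 and the output titles keep a name that the derivation does not match. Section 6 lists a change as small as an ACQ-6 category boundary, so by its own standard this difference belongs there.

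A reader might infer that any fall in reliever use would show up as fewer awakenings. The documents do not support that. The variable needs an awakening and rescue use upon it, so lower daytime use, or fewer puffs on waking, leaves it unchanged. Only a change in whether any rescue is used, given an awakening, moves it. If treatment made awakenings mild enough to need no reliever, that could be a genuine benefit, but it would not be fewer nights with an awakening.

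It is also fair that the night-time symptom score (SAP Section 3.6.2.1), recorded each morning regardless of rescue use, gives some cover for awakenings that the composite does not count. It does not isolate awakenings.

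**Conclusion.** The mismatch is established from the text alone. The named endpoint is not analysed, three outputs carry a label that does not describe their content, and the list of changes omits the difference.

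The size of any effect on the results is unknown. The range of −2 to −24 percentage points rests on assumed awakening rates of 20% to 60%, equal awakening rates in the two arms, and assumed differences in rescue use given an awakening. It shows that the mechanism works and does not predict what the trial would find. No single value from the table should be read as the expected bias, and if rescue use given an awakening is the same in all arms there is no spurious effect.

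A reader might also infer a threat to the trial's main conclusion. There is none: the endpoint is exploratory, it lies outside the testing hierarchy in SAP Section 4.1.1, and it is not an input to CompEx (SAP Section 3.4.6). The primary analysis and type I error are unaffected. This is a minor point that should be corrected because doing so is nearly free.

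**What to change.** - Derive the named endpoint as the 2-weekly percentage of nights with a yes to the awakening question, regardless of rescue use, under the completeness rule already in SAP Section 3.1.4.
- Keep the awakening-plus-rescue variable as an additional exploratory variable with its own label.
- Retitle Tables 14.2.10.1 and 14.2.10.2 and Figure 14.2.10 so that each title states which variable is shown and that it is a percentage of nights. Align the wording in SAP Table 1 and Section 3.1.1.
- Add one line to SAP Section 6 stating how the derived variables relate to the protocol's endpoint name.

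The cost is wording changes and one extra derivation. SAP Section 3.6.2 cites waking and rescue use as two separate diary questions, so no new data are needed.
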